6.10.6 Physical Examination

Physical Examinations will be assessed during Part I of this study at baseline and the Part I termination visit. For subjects who roll-over from study UX001-CL201 the baseline physical examination values may be derived from the last visit (week 48, or termination visit) in UX001-CL201, prior to participation in UX001-CL202.

Physical Examination will be assessed during Part II of this study at the Screening/Baseline and Months 1, 6, 18, 36, and termination visits. For subjects who roll-over from study UX001-CL201 and participate in Part I of this study the baseline physical examination values may be derived from the last visit in Part I (Part I termination visit). For Treatment

Naïve Subjects enrolled directly into Part II the baseline values will be the Screening/Baseline visit for these subjects.

Physical exam results for all subjects in the safety population will be reported in listing format. Changes in physical examination will be reported as adverse events.

6.10.7 Neurological Examination

Neurological Examinations will be assessed during Part I of this study at baseline and the Part I termination visit. For subjects who roll-over from study UX001-CL201 the baseline neurological examination values may be derived from the last visit (week 48, or termination visit) in UX001-CL201, prior to participation in UX001-CL202.

Neurological Examination will be assessed during Part II of this study at the Screening/Baseline and Months 6, 18, and 36 visits. For subjects who roll-over from study UX001-CL201 and participate in Part I of this study the baseline neurological examination values may be derived from the last visit in Part I (Part I termination visit). For Treatment Naïve Subjects enrolled directly into Part II the baseline values will be the Screening/Baseline visit for these subjects.

The neurological examination will include assessments of cognition, cranial nerves, motor function, coordination and gait, reflexes, and sensory function.

Neurological exam results for all subjects in the safety population will be reported in listing format. Changes in neurological examination will be reported as adverse events.

6.10.8 Pregnancy Testing

Results of pregnancy testing for females of child bearing potential will be provided in listings.

6.10.9 Other Safety Parameters

In some cases inferential statistical comparisons may be requested by the medical report writer (e.g., analysis of variance comparing vital signs or laboratory values between treatment groups). All such requests will be carried out by the statistician. P-values in such instances will serve as measures of distance to facilitate the clinical review and screening of these numerous variables.

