6 STATISTICAL METHODOLOGY

6.1 Sample Size

Approximately 46 subjects may be enrolled in Part I of this open-label extension study. Sample size is limited to the number of subjects enrolled in the Phase 2 safety and efficacy study, UX001-CL201, who achieve at least 80% treatment compliance and study visit completion. As Part I of the study is intended to evaluate the long-term safety of 6g/day SA-ER in subjects with GNE Myopathy and ascertain the long-term effect of SA-ER treatment on muscle strength, mobility, and functional disability, the sample size is deemed reasonable to satisfy Part I study objectives.

An additional 10 subjects will be enrolled into Part II of the study. This subset of treatment naïve GNE Myopathy subjects will provide additional safety and efficacy information following treatment with SA-ER/SA-IR. Note that more than 10 planned subjects may be enrolled in this subset of treatment naïve GNE Myopathy subjects, as new subjects are identified at the study centers. These additional subjects will only add additional information and informative value to this treatment naïve GNE Myopathy population. No modifications of updates to the SAP are needed for additional subjects in this group.

The study design is open-label with all subjects receiving the same treatment. Therefore, the study is not powered to assess statistically significant comparisons. Instead, the sample size is intended to provide the maximum amount of long-term safety and efficacy data for the investigational product.

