6.2 Randomization

This is an Open-Label Study where all subjects who roll over from study UX001-CL201 will receive 6g/day SA-ER in Part I and 12g/day SA-ER/SA-IR in Part II. Subjects enrolled into this study who are treatment naïve GNE Myopathy subjects will be included in Part II and receive 12g/day SA-ER/SA-IR. Since all subjects will receive the same treatment in Part II, randomization or blinding of study drug is not necessary. No randomization schedule or stratification strategy at baseline was developed for this study.

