6.10 Statistical Analysis: Safety

In general all safety analyses will be completed using descriptive summaries, graphs, and subject listings. No planned inferential testing of safety endpoints is planned. If after the any planned analysis it is determined by the medical writer and study medical monitor that inferential tests of significance may help to provide context for safety information these tests may be performed and identified in the CSR.

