6.10.1 Adverse Events

Adverse Events will be assessed at all visits and throughout the course of the study. The number and percent of subjects with any treatment-emergent adverse events (TEAEs) will be displayed by system organ class and preferred term for each treatment group (6g/day SA-ER, 12g/day SA-ER/SA-IR). Within each preferred term, subjects will be counted only once if they had more than one event reported during the treatment period. The same summary will be performed for all serious TEAEs and all TEAEs causing discontinuation of study drug.

The number and percent of subject TEAEs will also be summarized by greatest reported severity grade (Grades 1-5) for each event preferred term by treatment group. Wherever possible, the severity of all AEs observed will be graded using the NCI CTCAE (V4.0) as follows in [Table 9](#):

Table 9 NCI-CTCAE Common AE Grading Criteria

Grade	Description
1	Mild; asymptomatic or mild symptoms; clinical or diagnostic observations only; intervention not indicated.
2	Moderate; minimal, local or noninvasive intervention indicated; limiting age-appropriate instrumental ADL*.
3	Severe or medically significant but not immediately life-threatening; hospitalization or prolongation of hospitalization indicated; disabling; limiting self-care ADL**.
4	Life-threatening consequences; urgent intervention indicated.
5	Death related to AE.
Source: Common Terminology Criteria for Adverse Events (CTCAE), Version 4.0, Published May 28, 2009 (v4.03, June 24, 2010); USHHS/NIH/NCI * ADL=Activities for Daily Living: Instrumental ADL refer to preparing meals, shopping for groceries or clothes, using the telephone, managing money, etc. ** Self-care ADL refer to bathing, dressing and undressing, feeding self, using the toilet, taking medications, and not bedridden.	

The majority of AEs and TEAEs can be graded using the NCI-CTCAE system. Wherever possible, the severity of all AEs will be graded using the NCI CTCAE. The majority of AEs can be graded using this system. If an AE cannot be graded using the CTCAE criteria, it should be graded as mild, moderate, severe, life-threatening, or death using the definitions in Table 10.

Table 10 Mapped AE Grading Criteria

Grade	Description
Mild (Grade 1)	Awareness of signs or symptoms, but easily tolerated and of a minor irritant type, causing no loss of time from normal activities. Symptoms do not require therapy or a medical evaluation; signs and symptoms are transient.

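### The SAP's example of an on-request safety comparison, a between-group ANOVA of 6 g and 12 g values, ignores that most subjects are in both groups, so its p-values are mis-sized

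*SAP*

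**What the plan says.** SAP 6.10 makes safety analysis descriptive: "No planned inferential testing of safety endpoints is planned". SAP 6.10.9 then opens a route for tests on demand: "In some cases inferential statistical comparisons may be requested by the medical report writer". Its example is an "analysis of variance comparing vital signs or laboratory values between treatment groups". The section says that every such request will be carried out, and it gives the results a purpose: "P-values in such instances will serve as measures of distance to facilitate the clinical review and screening of these numerous variables".

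Section 6.10.9 does not define the groups. SAP 6.10.1 tabulates adverse events "for each treatment group (6g/day SA-ER, 12g/day SA-ER/SA-IR"), and SAP 6.6.4 and 6.10.5 use the same two groups. SAP 6.2 states who is in them: "all subjects who roll over from study UX001-CL201 will receive 6g/day SA-ER in Part I and 12g/day SA-ER/SA-IR in Part II". On numbers, SAP 6.1 has: "Approximately 46 subjects may be enrolled in Part I of this open-label extension study". It adds: "An additional 10 subjects will be enrolled into Part II of the study". The note to SAP Figure 1 says that some roll-overs went straight into Part II, without saying how many.

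Two roll-over safety baselines are on offer. SAP 5.3 uses the last UX001-CL201 assessment. SAP 6.10.2 and 6.10.3 also allow the Part I Termination value for Part II.

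**The concern.** The two dose groups are mostly one set of people measured first at 6 g and then at 12 g. A between-group ANOVA takes its error term from independent groups. With raw values it leaves all between-subject variation in the error, although that variation largely cancels when the same person is compared across doses. The p-value then answers a different question from the one of interest, which is whether values moved when these subjects changed dose.

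The p-values are meant for sorting through many variables. A p-value whose error depends on each variable's own within-subject correlation sorts them badly: a stable laboratory measure, where a small shift is easiest to see, is penalised most. SAP 6.10.2 and 6.10.3 plan listings only for laboratory and vital-sign data, so there are few other group-level views of how these values moved.

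**Working it through.** The documents give no standard deviation, effect size, correlation or power for this comparison, so there is no plan figure to reproduce. The within-subject correlation ρ is an assumption, shown as a range.

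**Inputs.** 46 subjects at 6 g; the same 46 plus 10 treatment-naive subjects at 12 g (SAP 6.1, 6.2), so the overlap is 46/56 = 82%. Two-sided 0.05 (SAP 6.5). SD 1 at each dose, equal correlation between visits, one visit per dose.

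**Raw values.** ANOVA takes the variance of the mean difference to be A = 1/46 + 1/56 = 0.03960. The true variance is T = A − 2ρ/56. The true size is 2[1 − Φ(1.96·√(A/T))]. At ρ = 0 this returns 5.0%, as it should. For 46 against the same 46, A = 2/46 and T = (1 − ρ)·2/46.

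| ρ | T (46 v 56) | 1.96·√(A/T) | Size, 46 v 56 | Size, 46 v 46 |
|---|---|---|---|---|
| 0.3 | 0.02888 | 2.295 | 2.2% | 1.9% |
| 0.5 | 0.02174 | 2.645 | 0.8% | 0.6% |
| 0.7 | 0.01460 | 3.228 | 0.13% | 0.04% |
| 0.8 | 0.01102 | 3.714 | 0.02% | <0.01% |

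Simulation of 46 v 56 (20,000 runs) agrees: 2.2%, 0.8%, 0.16% and 0.01%. Pooling 3 or 7 Part II visits per subject at ρ = 0.5 gives 0.9% and 1.0%, still conservative.

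**Power, raw values.** For a shift d, ANOVA power ≈ Φ((d − 1.96·√A)/√T). The paired test in the 46 has variance 2(1 − ρ)/46. At ρ = 0.7 and d = 0.3:

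- ANOVA: (0.3 − 1.96 × 0.1990)/0.1208 = −0.745, power 23%.
- Paired: 0.3/0.1142 − 1.96 = 0.667, power 75%; about 73% by simulation with the t-test.

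| ρ | ANOVA, 0.3 SD | Paired, 0.3 SD | ANOVA, 0.5 SD | Paired, 0.5 SD |
|---|---|---|---|---|
| 0.3 | 30% | 41% | 74% | 82% |
| 0.5 | 27% | 53% | 77% | 92% |
| 0.7 | 23% | 75% | 82% | 99% |
| 0.8 | 20% | 90% | 85% | >99% |

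These are normal approximations for 46 v 56. Using only the 46 in both groups lowers ANOVA power at ρ = 0.7 to 17% for 0.3 SD and about 78% for 0.5 SD.

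**Ranking.** ANOVA divides the correct z by √(A/T), which is 1.17 at ρ = 0.3 and 1.90 at ρ = 0.8. Two variables with the same correct z of, say, 2.5 would show z = 2.13 (p = 0.03) and z = 1.32 (p = 0.19).

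**Changes from baseline.** Under equal correlation each change has variance 2(1 − ρ), so in units of (1 − ρ), A = 2(1/46 + 1/56) = 0.07919.

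- Common UX001-CL201 baseline (SAP 5.3): the two changes share the baseline with the same sign, so their covariance is +1 and T = A − 2/56 = 0.04348. The critical value becomes 1.96 × 1.350 = 2.645 and size is 0.8% (about 0.9% simulated).
- Part-specific baselines (SAP 6.10.2, 6.10.3): the Part I Termination value enters the two changes with opposite signs, so their covariance is −1 and T = A + 2/56 = 0.11491. The critical value becomes 1.96 × 0.830 = 1.627 and size is 10.4% (about 10% simulated). If correlation decays between visits as AR(1), size is 5-9%.

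The direction of the error therefore depends on a choice that 6.10.9 leaves open.

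**The case against.** The strongest reply is that this attacks an illustration. No safety inference is planned, the ANOVA is one example of what might be requested, and Appendix 8.1 lists no such table for vital signs or safety laboratory values. This stands. A reader might infer that the ANOVA is the SAP's safety screen and the only means of detecting a shift at the higher dose. The documents do not support that. All values are listed by subject (SAP 6.10.2, 6.10.3), an abnormal laboratory finding can be an adverse event (protocol 8.5.1), and events are tabulated by dose (SAP 6.10.1). The DMC may review the 6-month data (SAP 6.3), shift tables are possible (SAP 6.5.4), and CK and free serum SA have GEE models (SAP 6.7.13, 6.9.1). Protocol 7.6.2 also plans laboratory summaries and changes from Baseline.

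Secondly, 6.10.9 does not say that pairing is ignored, and a repeated-measures ANOVA is still an ANOVA. SAP 5.1 also uses the term treatment groups for the UX001-CL201 dosing pathways, which contain different people. Both points are fair. But the other safety sections use 6 g and 12 g. Where the SAP intends to model repeated measures it says so (6.7.2), and it keeps ANCOVA largely for settings without them (6.7.3). An ordinary ANOVA across doses is the natural reading, and nothing in 6.10.9 prevents it.

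Thirdly, the correlation is unknown, the loss is modest at 0.3, and no screening cut-off is stated, so power at 0.05 is only a proxy for what is missed. All true; hence the range.

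Finally, pairing is no cure-all. Roll-overs who skipped Part I have no pair, and Part I always precedes Part II. These limits belong in the fix.

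**Conclusion.** The concern holds in limited form. If the example in SAP 6.10.9 is carried out as an ordinary ANOVA of 6 g against 12 g, its p-values are mis-sized. For raw values true size is about 2%, 0.6-0.8% and 0.1% at ρ = 0.3, 0.5 and 0.7. Power for a 0.3 SD shift at ρ = 0.7 is about 17-23% against about 73% paired. For a 0.5 SD shift it is about 78-82% against 99%, so the claim that moderate shifts would generally be passed over is not supported. Nor can the test be called conservative without qualification: with part-specific baselines its size can reach about 10%.

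These figures rest on 46 overlapping subjects, equal variances, the assumed correlation and, except where stated, equal correlation between visits. Fewer pairs reduce the overlap and the paired power. They apply to Parts I and II, which are all the SAP covers. The consequence is that an optional screening aid can miss or misrank shifts; it is not a failure of safety monitoring as a whole.

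**What to change.** In SAP 6.10.9, replace the ANOVA example with the following:

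- For any requested 6 g against 12 g comparison, analyse the within-subject change from the Part I Termination value to each Part II visit in roll-overs who have both values. Use a paired analysis or a mixed model with a subject effect.
- Name Part I Termination as the single baseline for this comparison, and report the mean change with its 95% CI.
- Report treatment-naive subjects, and roll-overs without a Part I value, separately as change from their own named baseline.
- State the limits: subjects without a Part I value leave the paired comparison, and a paired change does not separate dose from time because Part I always comes first.

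The cost is SAP wording only, since the values are already scheduled at Part I Termination and the Part II visits. The price is a somewhat smaller comparison set, by the treatment-naive subjects and an unstated number of roll-overs.

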8 APPENDICES

8.1 List of Prospective Tables and Figures

The following is a list of the planned Tables and Figures prospectively identified for the planned analyses described in this SAP. A separate document will be completed for programming specifications that provides details on the unique mock Tables, Figures, and Listings. The mock shells may be updated throughout the course of programming and review without amendment of this SAP.

Included is a list of the planned tables for this Study. Corresponding figures will be developed for those efficacy endpoints to display trends, frequencies, and modeled output were appropriate to better facilitate the understanding of the data and results. Note that additional tables and figures, not listed herein, may be generated to better understand study results. These additional tables and figures will be identified in the final publication of study results. The SAP will not be amended to identify additional analyses.

The final numbering and presentation order of the tables and figures completed to support the analyses conducted for UX001-CL202 will be determined prior to final delivery of the analyses. In general, clinical efficacy tables and figures will be grouped first by analysis type (as identified in [Table 8](#)), and then by endpoint.

Table ID⁽¹⁾	Table Description⁽²⁾
1	Subject Disposition
2	Demographics and Baseline Characteristics- Safety Population
3	Demographics and Baseline Characteristics- ITT Population
4	Number of Doses Administered- Safety Population
5	Number of Doses Administered- ITT Population
6	Prior Medication
7	Concomitant Medication
8	Interval History- Number of Falls
9	TEAE- Overall Summary

Table ID⁽¹⁾	Table Description⁽²⁾
10	TEAE- by SOC and PT (including second table of TEAE by descending frequency of PT)
11	Serious TEAE- by SOC and PT
12	TEAE Causing Discontinuation- by SOC and PT
13	TEAE by Severity- by SOC and PT
14	TEAE by Relationship- by SOC and PT
15	Elbow Extension (kg)- Summary
16	Elbow Extension (kg)- Primary Analysis #1
17	Elbow Extension (kg)- Primary Analysis #1- 6MWT >= 200
18	Elbow Extension (kg)- Primary Analysis #2
19	Elbow Extension (kg)- Primary Analysis #2- 6MWT >= 200
20	Elbow Extension (kg)- Primary Analysis #3
21	Elbow Extension (kg)- Primary Analysis #3- 6MWT >= 200
22	Elbow Extension (kg)- Secondary Analysis
23	Elbow Extension (kg)- Secondary Analysis- 6MWT >= 200
24	Elbow Extension (kg)- Treatment Naïve Primary Analysis
25	Elbow Extension (kg)- Treatment Naïve Secondary Analysis
26	Elbow Extension (kg)- Treatment Naïve Secondary Analysis- 6MWT >= 200
27	Elbow Flexion (kg)- Summary
28	Elbow Flexion (kg)- Primary Analysis #1
29	Elbow Flexion (kg)- Primary Analysis #1- 6MWT >= 200
30	Elbow Flexion (kg)- Primary Analysis #2
31	Elbow Flexion (kg)- Primary Analysis #2- 6MWT >= 200

Table ID⁽¹⁾	Table Description⁽²⁾
32	Elbow Flexion (kg)- Primary Analysis #3
33	Elbow Flexion (kg)- Primary Analysis #3- 6MWT >= 200
34	Elbow Flexion (kg)- Secondary Analysis
35	Elbow Flexion (kg)- Secondary Analysis- 6MWT >= 200
36	Elbow Flexion (kg)- Treatment Naïve Primary Analysis
37	Elbow Flexion (kg)- Treatment Naïve Secondary Analysis
38	Elbow Flexion (kg)- Treatment Naïve Secondary Analysis- 6MWT >= 200
39	Grip (kg)- Summary
40	Grip (kg)- Primary Analysis #1
41	Grip (kg)- Primary Analysis #1- 6MWT >= 200
42	Grip (kg)- Primary Analysis #2
43	Grip (kg)- Primary Analysis #2- 6MWT >= 200
44	Grip (kg)- Primary Analysis #3
45	Grip (kg)- Primary Analysis #3- 6MWT >= 200
46	Grip (kg)- Secondary Analysis
47	Grip (kg)- Secondary Analysis- 6MWT >= 200
48	Grip (kg)- Treatment Naïve Primary Analysis
49	Grip (kg)- Treatment Naïve Secondary Analysis
50	Grip (kg)- Treatment Naïve Secondary Analysis- 6MWT >= 200
51	Hip Abduction (kg)- Summary
52	Hip Abduction (kg)- Primary Analysis #1
53	Hip Abduction (kg)- Primary Analysis #1- 6MWT >= 200

Table ID⁽¹⁾	Table Description⁽²⁾
54	Hip Abduction (kg)- Primary Analysis #2
55	Hip Abduction (kg)- Primary Analysis #2- 6MWT >= 200
56	Hip Abduction (kg)- Primary Analysis #3
57	Hip Abduction (kg)- Primary Analysis #3- 6MWT >= 200
58	Hip Abduction (kg)- Secondary Analysis
59	Hip Abduction (kg)- Secondary Analysis- 6MWT >= 200
60	Hip Abduction (kg)- Treatment Naïve Primary Analysis
61	Hip Abduction (kg)- Treatment Naïve Secondary Analysis
62	Hip Abduction (kg)- Treatment Naïve Secondary Analysis- 6MWT >= 200
63	Hip Adduction (kg)- Summary
64	Hip Adduction (kg)- Primary Analysis #1
65	Hip Adduction (kg)- Primary Analysis #1- 6MWT >= 200
66	Hip Adduction (kg)- Primary Analysis #2
67	Hip Adduction (kg)- Primary Analysis #2- 6MWT >= 200
68	Hip Adduction (kg)- Primary Analysis #3
69	Hip Adduction (kg)- Primary Analysis #3- 6MWT >= 200
70	Hip Adduction (kg)- Secondary Analysis
71	Hip Adduction (kg)- Secondary Analysis- 6MWT >= 200
72	Hip Adduction (kg)- Treatment Naïve Primary Analysis
73	Hip Adduction (kg)- Treatment Naïve Secondary Analysis
74	Hip Adduction (kg)- Treatment Naïve Secondary Analysis- 6MWT >= 200
75	Hip Extension (kg)- Summary

Table ID⁽¹⁾	Table Description⁽²⁾
76	Hip Extension (kg)- Primary Analysis #1
77	Hip Extension (kg)- Primary Analysis #1- 6MWT >= 200
78	Hip Extension (kg)- Primary Analysis #2
79	Hip Extension (kg)- Primary Analysis #2- 6MWT >= 200
80	Hip Extension (kg)- Primary Analysis #3
81	Hip Extension (kg)- Primary Analysis #3- 6MWT >= 200
82	Hip Extension (kg)- Secondary Analysis
83	Hip Extension (kg)- Secondary Analysis- 6MWT >= 200
84	Hip Extension (kg)- Treatment Naïve Primary Analysis
85	Hip Extension (kg)- Treatment Naïve Secondary Analysis
86	Hip Extension (kg)- Treatment Naïve Secondary Analysis- 6MWT >= 200
87	Hip Flexion (kg)- Summary
88	Hip Flexion (kg)- Primary Analysis #1
89	Hip Flexion (kg)- Primary Analysis #1- 6MWT >= 200
90	Hip Flexion (kg)- Primary Analysis #2
91	Hip Flexion (kg)- Primary Analysis #2- 6MWT >= 200
92	Hip Flexion (kg)- Primary Analysis #3
93	Hip Flexion (kg)- Primary Analysis #3- 6MWT >= 200
94	Hip Flexion (kg)- Secondary Analysis
95	Hip Flexion (kg)- Secondary Analysis- 6MWT >= 200
96	Hip Flexion (kg)- Treatment Naïve Primary Analysis
97	Hip Flexion (kg)- Treatment Naïve Secondary Analysis

Table ID⁽¹⁾	Table Description⁽²⁾
98	Hip Flexion (kg)- Treatment Naïve Secondary Analysis- 6MWT >= 200
99	Key (kg)- Summary
100	Key (kg)- Primary Analysis #1
101	Key (kg)- Primary Analysis #1- 6MWT >= 200
102	Key (kg)- Primary Analysis #2
103	Key (kg)- Primary Analysis #2- 6MWT >= 200
104	Key (kg)- Primary Analysis #3
105	Key (kg)- Primary Analysis #3- 6MWT >= 200
106	Key (kg)- Secondary Analysis
107	Key (kg)- Secondary Analysis- 6MWT >= 200
108	Key (kg)- Treatment Naïve Primary Analysis
109	Key (kg)- Treatment Naïve Secondary Analysis
110	Key (kg)- Treatment Naïve Secondary Analysis- 6MWT >= 200
111	Knee Extension (kg)- Summary
112	Knee Extension (kg)- Primary Analysis #1
113	Knee Extension (kg)- Primary Analysis #1- 6MWT >= 200
114	Knee Extension (kg)- Primary Analysis #2
115	Knee Extension (kg)- Primary Analysis #2- 6MWT >= 200
116	Knee Extension (kg)- Primary Analysis #3
117	Knee Extension (kg)- Primary Analysis #3- 6MWT >= 200
118	Knee Extension (kg)- Secondary Analysis
119	Knee Extension (kg)- Secondary Analysis- 6MWT >= 200

Table ID⁽¹⁾	Table Description⁽²⁾
120	Knee Extension (kg)- Treatment Naïve Primary Analysis
121	Knee Extension (kg)- Treatment Naïve Secondary Analysis
122	Knee Extension (kg)- Treatment Naïve Secondary Analysis- 6MWT >= 200
123	Knee Flexion (kg)- Summary
124	Knee Flexion (kg)- Primary Analysis #1
125	Knee Flexion (kg)- Primary Analysis #1- 6MWT >= 200
126	Knee Flexion (kg)- Primary Analysis #2
127	Knee Flexion (kg)- Primary Analysis #2- 6MWT >= 200
128	Knee Flexion (kg)- Primary Analysis #3
129	Knee Flexion (kg)- Primary Analysis #3- 6MWT >= 200
130	Knee Flexion (kg)- Secondary Analysis
131	Knee Flexion (kg)- Secondary Analysis- 6MWT >= 200
132	Knee Flexion (kg)- Treatment Naïve Primary Analysis
133	Knee Flexion (kg)- Treatment Naïve Secondary Analysis
134	Knee Flexion (kg)- Treatment Naïve Secondary Analysis- 6MWT >= 200
135	Palmar (kg)- Summary
136	Palmar (kg)- Primary Analysis #1
137	Palmar (kg)- Primary Analysis #1- 6MWT >= 200
138	Palmar (kg)- Primary Analysis #2
139	Palmar (kg)- Primary Analysis #2- 6MWT >= 200
140	Palmar (kg)- Primary Analysis #3
141	Palmar (kg)- Primary Analysis #3- 6MWT >= 200

Table ID⁽¹⁾	Table Description⁽²⁾
142	Palmar (kg)- Secondary Analysis
143	Palmar (kg)- Secondary Analysis- 6MWT >= 200
144	Palmar (kg)- Treatment Naïve Primary Analysis
145	Palmar (kg)- Treatment Naïve Secondary Analysis
146	Palmar (kg)- Treatment Naïve Secondary Analysis- 6MWT >= 200
147	Shoulder Abduction (kg)- Summary
148	Shoulder Abduction (kg)- Primary Analysis #1
149	Shoulder Abduction (kg)- Primary Analysis #1- 6MWT >= 200
150	Shoulder Abduction (kg)- Primary Analysis #2
151	Shoulder Abduction (kg)- Primary Analysis #2- 6MWT >= 200
152	Shoulder Abduction (kg)- Primary Analysis #3
153	Shoulder Abduction (kg)- Primary Analysis #3- 6MWT >= 200
154	Shoulder Abduction (kg)- Secondary Analysis
155	Shoulder Abduction (kg)- Secondary Analysis- 6MWT >= 200
156	Shoulder Abduction (kg)- Treatment Naïve Primary Analysis
157	Shoulder Abduction (kg)- Treatment Naïve Secondary Analysis
158	Shoulder Abduction (kg)- Treatment Naïve Secondary Analysis- 6MWT >= 200
159	Tip (kg)- Summary
160	Tip (kg)- Primary Analysis #1
161	Tip (kg)- Primary Analysis #1- 6MWT >= 200
162	Tip (kg)- Primary Analysis #2
163	Tip (kg)- Primary Analysis #2- 6MWT >= 200

Table ID⁽¹⁾	Table Description⁽²⁾
164	Tip (kg)- Primary Analysis #3
165	Tip (kg)- Primary Analysis #3- 6MWT >= 200
166	Tip (kg)- Secondary Analysis
167	Tip (kg)- Secondary Analysis- 6MWT >= 200
168	Tip (kg)- Treatment Naïve Primary Analysis
169	Tip (kg)- Treatment Naïve Secondary Analysis
170	Tip (kg)- Treatment Naïve Secondary Analysis- 6MWT >= 200
171	HHD Upper Extremity CS- Summary
172	HHD Upper Extremity CS- Primary Analysis #1
173	HHD Upper Extremity CS- Primary Analysis #1- 6MWT >= 200
174	HHD Upper Extremity CS- Primary Analysis #2
175	HHD Upper Extremity CS- Primary Analysis #2- 6MWT >= 200
176	HHD Upper Extremity CS- Primary Analysis #3
177	HHD Upper Extremity CS- Primary Analysis #3- 6MWT >= 200
178	HHD Upper Extremity CS- Secondary Analysis
179	HHD Upper Extremity CS- Secondary Analysis- 6MWT >= 200
180	HHD Upper Extremity CS- Treatment Naïve Primary Analysis
181	HHD Upper Extremity CS- Treatment Naïve Secondary Analysis
182	HHD Upper Extremity CS- Treatment Naïve Secondary Analysis- 6MWT >= 200
183	HHD Lower Extremity CS- Summary
184	HHD Lower Extremity CS- Primary Analysis #1
185	HHD Lower Extremity CS- Primary Analysis #1- 6MWT >= 200

Table ID⁽¹⁾	Table Description⁽²⁾
186	HHD Lower Extremity CS- Primary Analysis #2
187	HHD Lower Extremity CS- Primary Analysis #2- 6MWT >= 200
188	HHD Lower Extremity CS- Primary Analysis #3
189	HHD Lower Extremity CS- Primary Analysis #3- 6MWT >= 200
190	HHD Lower Extremity CS- Secondary Analysis
191	HHD Lower Extremity CS- Secondary Analysis- 6MWT >= 200
192	HHD Lower Extremity CS- Treatment Naïve Primary Analysis
193	HHD Lower Extremity CS- Treatment Naïve Secondary Analysis
194	HHD Lower Extremity CS- Treatment Naïve Secondary Analysis- 6MWT >= 200
195	6MWT- Summary
196	6MWT- Primary Analysis #1
197	6MWT- Primary Analysis #1- 6MWT >= 200
198	6MWT- Primary Analysis #2
199	6MWT- Primary Analysis #2- 6MWT >= 200
200	6MWT- Primary Analysis #3
201	6MWT- Primary Analysis #3- 6MWT >= 200
202	6MWT- Secondary Analysis
203	6MWT- Secondary Analysis- 6MWT >= 200
204	6MWT- Treatment Naïve Primary Analysis
205	6MWT- Treatment Naïve Secondary Analysis
206	6MWT- Treatment Naïve Secondary Analysis- 6MWT >= 200
207	Comfortable Gait Speed- Summary

Table ID⁽¹⁾	Table Description⁽²⁾
208	Comfortable Gait Speed- Primary Analysis #1
209	Comfortable Gait Speed- Primary Analysis #1- 6MWT >= 200
210	Comfortable Gait Speed- Primary Analysis #2
211	Comfortable Gait Speed- Primary Analysis #2- 6MWT >= 200
212	Comfortable Gait Speed- Primary Analysis #3
213	Comfortable Gait Speed- Primary Analysis #3- 6MWT >= 200
214	Comfortable Gait Speed- Secondary Analysis
215	Comfortable Gait Speed- Secondary Analysis- 6MWT >= 200
216	Comfortable Gait Speed- Treatment Naïve Primary Analysis
217	Comfortable Gait Speed- Treatment Naïve Secondary Analysis
218	Comfortable Gait Speed- Treatment Naïve Secondary Analysis- 6MWT >= 200
219	Maximum Gait Speed- Summary
220	Maximum Gait Speed- Primary Analysis #1
221	Maximum Gait Speed- Primary Analysis #1- 6MWT >= 200
222	Maximum Gait Speed- Primary Analysis #2
223	Maximum Gait Speed- Primary Analysis #2- 6MWT >= 200
224	Maximum Gait Speed- Primary Analysis #3
225	Maximum Gait Speed- Primary Analysis #3- 6MWT >= 200
226	Maximum Gait Speed- Secondary Analysis
227	Maximum Gait Speed- Secondary Analysis- 6MWT >= 200
228	Maximum Gait Speed- Treatment Naïve Primary Analysis
229	Maximum Gait Speed- Treatment Naïve Secondary Analysis

Table ID⁽¹⁾	Table Description⁽²⁾
230	Maximum Gait Speed- Treatment Naïve Secondary Analysis- 6MWT >= 200
231	Weighted Arm Lift- Summary
232	Weighted Arm Lift- Primary Analysis #1
233	Weighted Arm Lift- Primary Analysis #1- 6MWT >= 200
234	Weighted Arm Lift- Primary Analysis #2
235	Weighted Arm Lift- Primary Analysis #2- 6MWT >= 200
236	Weighted Arm Lift- Primary Analysis #3
237	Weighted Arm Lift- Primary Analysis #3- 6MWT >= 200
238	Weighted Arm Lift- Secondary Analysis
239	Weighted Arm Lift- Secondary Analysis- 6MWT >= 200
240	Weighted Arm Lift- Treatment Naïve Primary Analysis
241	Weighted Arm Lift- Treatment Naïve Secondary Analysis
242	Weighted Arm Lift- Treatment Naïve Secondary Analysis- 6MWT >= 200
243	Elbow Extension (kg)- % Predicted- Summary
244	Elbow Extension (kg)- % Predicted- Primary Analysis #1
245	Elbow Extension (kg)- % Predicted- Primary Analysis #1- 6MWT >= 200
246	Elbow Extension (kg)- % Predicted- Primary Analysis #2
247	Elbow Extension (kg)- % Predicted- Primary Analysis #2- 6MWT >= 200
248	Elbow Extension (kg)- % Predicted- Primary Analysis #3
249	Elbow Extension (kg)- % Predicted- Primary Analysis #3- 6MWT >= 200
250	Elbow Extension (kg)- % Predicted- Secondary Analysis
251	Elbow Extension (kg)- % Predicted- Secondary Analysis- 6MWT >= 200

Table ID⁽¹⁾	Table Description⁽²⁾
252	Elbow Extension (kg)- % Predicted- Treatment Naïve Primary Analysis
253	Elbow Extension (kg)- % Predicted- Treatment Naïve Secondary Analysis
254	Elbow Extension (kg)- % Predicted- Treatment Naïve Secondary Analysis- 6MWT >= 200
255	Elbow Flexion (kg)- % Predicted- Summary
256	Elbow Flexion (kg)- % Predicted- Primary Analysis #1
257	Elbow Flexion (kg)- % Predicted- Primary Analysis #1- 6MWT >= 200
258	Elbow Flexion (kg)- % Predicted- Primary Analysis #2
259	Elbow Flexion (kg)- % Predicted- Primary Analysis #2- 6MWT >= 200
260	Elbow Flexion (kg)- % Predicted- Primary Analysis #3
261	Elbow Flexion (kg)- % Predicted- Primary Analysis #3- 6MWT >= 200
262	Elbow Flexion (kg)- % Predicted- Secondary Analysis
263	Elbow Flexion (kg)- % Predicted- Secondary Analysis- 6MWT >= 200
264	Elbow Flexion (kg)- % Predicted- Treatment Naïve Primary Analysis
265	Elbow Flexion (kg)- % Predicted- Treatment Naïve Secondary Analysis
266	Elbow Flexion (kg)- % Predicted- Treatment Naïve Secondary Analysis- 6MWT >= 200
267	Grip (kg)- % Predicted- Summary
268	Grip (kg)- % Predicted- Primary Analysis #1
269	Grip (kg)- % Predicted- Primary Analysis #1- 6MWT >= 200
270	Grip (kg)- % Predicted- Primary Analysis #2
271	Grip (kg)- % Predicted- Primary Analysis #2- 6MWT >= 200
272	Grip (kg)- % Predicted- Primary Analysis #3
273	Grip (kg)- % Predicted- Primary Analysis #3- 6MWT >= 200

Table ID⁽¹⁾	Table Description⁽²⁾
274	Grip (kg)- % Predicted- Secondary Analysis
275	Grip (kg)- % Predicted- Secondary Analysis- 6MWT >= 200
276	Grip (kg)- % Predicted- Treatment Naïve Primary Analysis
277	Grip (kg)- % Predicted- Treatment Naïve Secondary Analysis
278	Grip (kg)- % Predicted- Treatment Naïve Secondary Analysis- 6MWT >= 200
279	Hip Abduction (kg)- % Predicted- Summary
280	Hip Abduction (kg)- % Predicted- Primary Analysis #1
281	Hip Abduction (kg)- % Predicted- Primary Analysis #1- 6MWT >= 200
282	Hip Abduction (kg)- % Predicted- Primary Analysis #2
283	Hip Abduction (kg)- % Predicted- Primary Analysis #2- 6MWT >= 200
284	Hip Abduction (kg)- % Predicted- Primary Analysis #3
285	Hip Abduction (kg)- % Predicted- Primary Analysis #3- 6MWT >= 200
286	Hip Abduction (kg)- % Predicted- Secondary Analysis
287	Hip Abduction (kg)- % Predicted- Secondary Analysis- 6MWT >= 200
288	Hip Abduction (kg)- % Predicted- Treatment Naïve Primary Analysis
289	Hip Abduction (kg)- % Predicted- Treatment Naïve Secondary Analysis
290	Hip Abduction (kg)- % Predicted- Treatment Naïve Secondary Analysis- 6MWT >= 200
291	Hip Adduction (kg)- % Predicted- Summary
292	Hip Adduction (kg)- % Predicted- Primary Analysis #1
293	Hip Adduction (kg)- % Predicted- Primary Analysis #1- 6MWT >= 200
294	Hip Adduction (kg)- % Predicted- Primary Analysis #2
295	Hip Adduction (kg)- % Predicted- Primary Analysis #2- 6MWT >= 200

Table ID⁽¹⁾	Table Description⁽²⁾
296	Hip Adduction (kg)- % Predicted- Primary Analysis #3
297	Hip Adduction (kg)- % Predicted- Primary Analysis #3- 6MWT >= 200
298	Hip Adduction (kg)- % Predicted- Secondary Analysis
299	Hip Adduction (kg)- % Predicted- Secondary Analysis- 6MWT >= 200
300	Hip Adduction (kg)- % Predicted- Treatment Naïve Primary Analysis
301	Hip Adduction (kg)- % Predicted- Treatment Naïve Secondary Analysis
302	Hip Adduction (kg)- % Predicted- Treatment Naïve Secondary Analysis- 6MWT >= 200
303	Hip Extension (kg)- % Predicted- Summary
304	Hip Extension (kg)- % Predicted- Primary Analysis #1
305	Hip Extension (kg)- % Predicted- Primary Analysis #1- 6MWT >= 200
306	Hip Extension (kg)- % Predicted- Primary Analysis #2
307	Hip Extension (kg)- % Predicted- Primary Analysis #2- 6MWT >= 200
308	Hip Extension (kg)- % Predicted- Primary Analysis #3
309	Hip Extension (kg)- % Predicted- Primary Analysis #3- 6MWT >= 200
310	Hip Extension (kg)- % Predicted- Secondary Analysis
311	Hip Extension (kg)- % Predicted- Secondary Analysis- 6MWT >= 200
312	Hip Extension (kg)- % Predicted- Treatment Naïve Primary Analysis
313	Hip Extension (kg)- % Predicted- Treatment Naïve Secondary Analysis
314	Hip Extension (kg)- % Predicted- Treatment Naïve Secondary Analysis- 6MWT >= 200
315	Hip Flexion (kg)- % Predicted- Summary
316	Hip Flexion (kg)- % Predicted- Primary Analysis #1
317	Hip Flexion (kg)- % Predicted- Primary Analysis #1- 6MWT >= 200

Table ID⁽¹⁾	Table Description⁽²⁾
318	Hip Flexion (kg)- % Predicted- Primary Analysis #2
319	Hip Flexion (kg)- % Predicted- Primary Analysis #2- 6MWT >= 200
320	Hip Flexion (kg)- % Predicted- Primary Analysis #3
321	Hip Flexion (kg)- % Predicted- Primary Analysis #3- 6MWT >= 200
322	Hip Flexion (kg)- % Predicted- Secondary Analysis
323	Hip Flexion (kg)- % Predicted- Secondary Analysis- 6MWT >= 200
324	Hip Flexion (kg)- % Predicted- Treatment Naïve Primary Analysis
325	Hip Flexion (kg)- % Predicted- Treatment Naïve Secondary Analysis
326	Hip Flexion (kg)- % Predicted- Treatment Naïve Secondary Analysis- 6MWT >= 200
327	Key (kg)- % Predicted- Summary
328	Key (kg)- % Predicted- Primary Analysis #1
329	Key (kg)- % Predicted- Primary Analysis #1- 6MWT >= 200
330	Key (kg)- % Predicted- Primary Analysis #2
331	Key (kg)- % Predicted- Primary Analysis #2- 6MWT >= 200
332	Key (kg)- % Predicted- Primary Analysis #3
333	Key (kg)- % Predicted- Primary Analysis #3- 6MWT >= 200
334	Key (kg)- % Predicted- Secondary Analysis
335	Key (kg)- % Predicted- Secondary Analysis- 6MWT >= 200
336	Key (kg)- % Predicted- Treatment Naïve Primary Analysis
337	Key (kg)- % Predicted- Treatment Naïve Secondary Analysis
338	Key (kg)- % Predicted- Treatment Naïve Secondary Analysis- 6MWT >= 200
339	Knee Extension (kg)- % Predicted- Summary

Table ID⁽¹⁾	Table Description⁽²⁾
340	Knee Extension (kg)- % Predicted- Primary Analysis #1
341	Knee Extension (kg)- % Predicted- Primary Analysis #1- 6MWT >= 200
342	Knee Extension (kg)- % Predicted- Primary Analysis #2
343	Knee Extension (kg)- % Predicted- Primary Analysis #2- 6MWT >= 200
344	Knee Extension (kg)- % Predicted- Primary Analysis #3
345	Knee Extension (kg)- % Predicted- Primary Analysis #3- 6MWT >= 200
346	Knee Extension (kg)- % Predicted- Secondary Analysis
347	Knee Extension (kg)- % Predicted- Secondary Analysis- 6MWT >= 200
348	Knee Extension (kg)- % Predicted- Treatment Naïve Primary Analysis
349	Knee Extension (kg)- % Predicted- Treatment Naïve Secondary Analysis
350	Knee Extension (kg)- % Predicted- Treatment Naïve Secondary Analysis- 6MWT >= 200
351	Knee Flexion (kg)- % Predicted- Summary
352	Knee Flexion (kg)- % Predicted- Primary Analysis #1
353	Knee Flexion (kg)- % Predicted- Primary Analysis #1- 6MWT >= 200
354	Knee Flexion (kg)- % Predicted- Primary Analysis #2
355	Knee Flexion (kg)- % Predicted- Primary Analysis #2- 6MWT >= 200
356	Knee Flexion (kg)- % Predicted- Primary Analysis #3
357	Knee Flexion (kg)- % Predicted- Primary Analysis #3- 6MWT >= 200
358	Knee Flexion (kg)- % Predicted- Secondary Analysis
359	Knee Flexion (kg)- % Predicted- Secondary Analysis- 6MWT >= 200
360	Knee Flexion (kg)- % Predicted- Treatment Naïve Primary Analysis
361	Knee Flexion (kg)- % Predicted- Treatment Naïve Secondary Analysis

Table ID⁽¹⁾	Table Description⁽²⁾
362	Knee Flexion (kg)- % Predicted- Treatment Naïve Secondary Analysis- 6MWT >= 200
363	Palmar (kg)- % Predicted- Summary
364	Palmar (kg)- % Predicted- Primary Analysis #1
365	Palmar (kg)- % Predicted- Primary Analysis #1- 6MWT >= 200
366	Palmar (kg)- % Predicted- Primary Analysis #2
367	Palmar (kg)- % Predicted- Primary Analysis #2- 6MWT >= 200
368	Palmar (kg)- % Predicted- Primary Analysis #3
369	Palmar (kg)- % Predicted- Primary Analysis #3- 6MWT >= 200
370	Palmar (kg)- % Predicted- Secondary Analysis
371	Palmar (kg)- % Predicted- Secondary Analysis- 6MWT >= 200
372	Palmar (kg)- % Predicted- Treatment Naïve Primary Analysis
373	Palmar (kg)- % Predicted- Treatment Naïve Secondary Analysis
374	Palmar (kg)- % Predicted- Treatment Naïve Secondary Analysis- 6MWT >= 200
375	Shoulder Abduction (kg)- % Predicted- Summary
